#### **Visit 3 week 2, prior to surgery (37 minutes)**

- Review of possible adverse events.
- Participants will have a maximum of 12.5ml peripheral blood taken. This blood will be transported to the central laboratory for assessment of levels of adalimumab and antibodies to adalimumab.
- The injection site will be assessed to monitor for local adverse effects using an injection site response form.
- Participants will have ultrasound scan to assess the size of the injected nodule.
- A digital photograph of the palm showing the selected nodule will be recorded.
- The hardness of the palmar tissue overlying the Dupuytren's nodule will be measured using tonometry.

Following the **standard care pathway**, participants will have surgery under general anaesthetic or regional block and the excised Dupuytren's tissue, which is normally discarded, will be collected and sent to the central laboratory for analysis (See 8.7 Sample handling). The samples will be collected and transported as per the Sampling handling protocol.

Participants will continue to follow the standard care pathway following surgery for DD.

#### **Visit 4 (2 weeks after surgery) (12 minutes) + standard consultation time**

Following the standard care pathway following surgery for DD, participants will be reviewed in the hand clinic on an outpatient basis. If non-dissolvable sutures have been used, they will be removed at this stage.

- Review of possible adverse events.
- The participant's wound will be assessed.
- A digital photograph of the palm will be recorded.

#### **Visit 5 (12 weeks after surgery) (15 minutes) + standard consultation time**

Following the standard care pathway following surgery for DD, participants will be reviewed in the outpatient hand clinic.

- Review of possible adverse events.
- Participants will complete a Health Quality of Life Questionnaire, the EQ-5D-5L.

#### **Part 2 Randomised Controlled Trial**

One week after the first treatment, participants will be phoned by a member of site staff to monitor for adverse events. If any of the information provided by the participant indicates that there may be a

problem with the hand that was injected this is to be brought to the urgent attention of the local PI, or other clinician on the site delegation log.

**Visit 3, 3 months (post baseline visit) (1 hour 47 minutes)**

- Review of possible adverse events.
- Participants will have a maximum of 12.5ml peripheral blood taken. This blood will be transported to the central laboratory for assessment of levels of adalimumab and antibodies to adalimumab.
- Participants will have an ultrasound scan to assess the size (grey scale) of the previously injected nodule.
- The injected nodule will be clinically assessed for suitability for injection.
- The hardness of the palmar tissue overlying the Dupuytren's nodule will be measured using tonometry.
- A digital photograph of the palm showing the selected nodule and indicating the nodule and associated affected finger will be recorded.
- Participants will have their finger range of movement measured using a goniometer.
- Grip strength will be measured using a JAMAR Dynamometer.
- Ametop gel or lidocaine/prilocaine cream may be applied 30 minutes to 1 hour prior to injection.
- Participants will complete the MHQ hand function questionnaire, and a Health Quality of Life Questionnaire, the EQ-5D-5L, and the Resource Use Questionnaire. Participants will consider the activity most restricted by DD identified at baseline and score it on a scale of 1-10.
- The injection will be administered into the previously injected Dupuytren's nodule (unless the clinician is not satisfied they can accurately deliver a repeat injection).
- Participants will then answer 2 questions about the experience of the injection.
- The injection site will be assessed by a trial healthcare professional blinded to treatment allocation to monitor for local adverse effects using an injection site response form.

**Visit 4, 6 months and**

**Visit 5, 9 months (1 hour 42 minutes)**

Both visits 4 and 5 are the same as visit 3 except that **no** blood will be drawn at these visits.

**Visit 6, 12 months (57 minutes)**

- Review of possible adverse events.
- Participants will have an ultrasound scan to assess the size (grey scale) of the injected nodule.
- The injected nodule will be clinically assessed.
- Participants will have a maximum of 12.5ml peripheral blood taken. This blood will be transported to the central laboratory for assessment of levels of adalimumab and antibodies to adalimumab.
- The hardness of the palmar tissue overlying the Dupuytren's nodule will be measured using tonometry.
- A digital photograph of the palm showing the selected nodule and indicating the nodule and associated affected finger will be recorded.
- Participants will have their affected finger range of movement measured using a goniometer.
- Grip strength will be measured using a JAMAR Dynamometer.
- Participants will complete the MHQ hand function questionnaire, and a Health Quality of Life Questionnaire, the EQ-5D-5L and the Resource Use Questionnaire. Participants will consider the activity most restricted by DD identified at baseline and score it on a scale of 1-10.

**Visit 7, 18 months (52 minutes)**

- Review of possible adverse events.
- Participants will have an ultrasound scan to assess the size (grey scale) of the injected nodule.
- The injected nodule will be clinically assessed.
- The hardness of the palmar tissue overlying the Dupuytren's nodule will be measured using tonometry.
- A digital photograph of the palm showing the selected nodule will be recorded.
- Participants will have their finger range of movement measured using a goniometer.
- Grip strength will be measured using a JAMAR Dynamometer.
- Participants will complete the MHQ hand function questionnaire, and a Health Quality of Life Questionnaire, the EQ-5D-5L and the Resource Use Questionnaire. Participants will consider the activity most restricted by DD identified at baseline and score it on a scale of 1-10.
- Any progression to surgery of the digit being assessed will be recorded.

If a participant is unable or unwilling to attend a follow up appointment but happy to complete the questionnaires, the questionnaires may be provided to the participant by email or post for completion. Other follow up data such as progression to surgery can also be collected by telephone and/or from the medical notes. The site must also check with the participant for any AE or SAE that require to be reported (if applicable) and submit the relevant CRF(s) as required.

### 8.7. Sample Handling

**Part 1** only.

**Tissue:** All tissue (removed during surgery) will be analysed in laboratories within the Nuffield Department of Orthopaedics, Rheumatology and Musculoskeletal Sciences (NDORMS), University of Oxford, in Oxford, UK. Following surgery, the anonymised tissue samples will be transported as per instructions specified in a Sample Handling Manual to NDORMS laboratories. A scientist not involved with the clinical assessment will dissect the nodule and extract the mRNA and protein. PCR will be carried out as previously described (Verjee et al., 2013). Protein levels will be measured using electrochemiluminescence (Meso Scale Diagnostics, Maryland, USA) or other validated assays in accordance with manufacturer's instructions or published protocols. The scientist will be blinded to treatment allocation.

**Part 1 and Part 2**

**Blood:** The participants in the trial will have:

**Part 1:** A maximum of 12.5ml of blood collected at baseline and 2 weeks post-injection will be sent to the NDORMS laboratories in Oxford.

**Part 2:** A maximum of 12.5ml of blood collected at baseline, 3 months, and 12 months post first injection, will be sent to the NDORMS laboratories, in Oxford.

The transportation procedure is described in the Sample Handling Manual. On arrival the serum will be stored at -80 degrees Celsius. Serum concentration of adalimumab and antibodies to adalimumab will be measured using a commercial ELISA kit.

Participants will have provided informed consent approving collection, long-term storage, and future use of tissue and blood. As new mechanisms of action, safety and efficacy may evolve during or following the trial, which are unknown at present, biospecimens will be stored for a maximum of 15 years from the end of trial, after which time they will be destroyed. All samples will be identified by a trial identification number and stored securely.

#### **8.8. Discontinuation/Withdrawal of Participants from Trial or Trial Treatment**

Each participant has the right to withdraw from the study treatment at any time. In addition, the investigator may discontinue a participant from the study treatment at any time if the investigator considers it necessary for any reason including:

- Pregnancy
- Significant protocol deviation
- Significant non-compliance with treatment regimen or study requirements
- An adverse event which requires discontinuation of the study medication or results in inability to continue to comply with study procedures
- Hand surgery to remove the nodule being treated.

The reason for withdrawal will be recorded in the CRF. Following withdrawal from study treatment, participants will be encouraged to continue to attend for follow up appointments.

In the event that a participant were to undergo intervention (e.g. surgical excision, PNF, collagenase) to the digit/ray with the treated nodule during the course of the trial, the participant should be encouraged to attend the next follow up appointment. However, physical measures, including tonometry, range of motion and ultrasound assessments are not required (note: hand photograph is required). They should also be encouraged to attend the 12 month follow up appointment so that a blood sample can be obtained. Should the participant have further follow up appointments due (after attending the subsequent and 12 month appointments), or be unwilling to attend for a follow up appointment but agree to complete the questionnaires, the questionnaires may be provided to the participant by email or post for completion. The site must also ensure that any AE or SAE for which reporting is required are identified and submit the relevant CRF(s) as required.

Note: In the event that the participant undergoes surgery to a digit other than the one being treated in the trial, trial treatment and follow up should continue as per protocol.

##### **Part 1**

Participants may withdraw consent from the study at any time and will continue on the standard care pathway of hand surgery and aftercare. Participants who do not proceed to surgery may be replaced if this occurs during the recruitment phase of [Part 1](#).

##### **Part 2**

Participants may withdraw consent from the study at any time and will continue on the standard care.

##### **Part 1 and Part 2**

Information collected up to the point of withdrawal may still be used. To monitor safety, if the participant withdraws after they have received medication their medical notes may be reviewed for the usual follow-

up period to capture protocol required safety data (i.e. grade 3 or above AE) . Intention-to-treat analyses will be carried out requiring admission of data to analysis for participants that are withdrawn.

#### **8.9. Definition of End of Trial**

The end of trial for each part of the study is the date of the last visit of the last participant. The overall end of the trial is the last visit of the last participant in part 2, or if the last participant is unable/unwilling to attend, the date of receipt of their completed questionnaires.

### **9. INVESTIGATIONAL MEDICINAL PRODUCTS (IMP)**

#### **9.1. IMP Description**

Adalimumab is a human monoclonal antibody with Marketing Authorisation, but will be used off-label for this study. Adalimumab is available as both a 40 mg in 0.8 ml formulation, and (as of 2016), a 40 mg in 0.4 ml formulation. These formulations differ in the excipients they contain, with the 40 mg in 0.4 ml containing only polysorbate 80 and mannitol, and the 40 mg in 0.8 ml contains several other excipients, including citrate.. The 40 mg/0.8 ml formulation will be supplied in a single use glass vial and this can be used to provide variable doses lower than 40 mg. At the time of writing, the 40 mg/0.4 ml formulation is not available as a single use glass vial and so will be supplied in a pre-filled syringe. If during the trial, it becomes possible to obtain single use glass vials for this formulation then these may be used instead. Normal saline will be used as placebo. The cost of the drug will be paid for by 180 Therapeutics LP.

#### **9.2. Storage and labelling of IMP**

The adalimumab IMP will be purchased from AbbVie Ltd by the sites participating in the study. Pharmacy will receive the trial supply and label it 'For clinical trial use only' with other details such as the name of the investigator, sponsor and EudraCT number. No special packaging/blinding will be required as the person collecting and preparing the drug will not be blinded as described in section 8.4. It will be stored according to the manufacturer's recommendations in a refrigerator at 2°C to 8°C in the original container, protected from light, until it is used.

The saline IMP will be purchased by the site and similarly labelled and stored in a refrigerator at 2°C to 8°C.

The IMP will be issued on prescription.

#### **9.3. Preparation of IMP**

The pre-filled syringe is fitted with a non-removable fine gauge needle and the research team have found that extremely high pressures are required to inject directly into the fibrotic nodule of Dupuytren's disease. Participants experience a lot of pain as a result and it is possible that the injection through a small calibre needle at high pressures may denature the adalimumab.

To prevent these problems, the IMP will be ejected into the barrel of an empty 1ml syringe the plunger of which has been withdrawn sufficiently to accommodate the volume of adalimumab [0.4 ml]. This

procedure will be performed by an experienced medically qualified practitioner, who will ensure sterility throughout by following a no-touch technique for the contents of the barrel of the syringe. An appropriate gauge needle (typically 25 gauge) will be fitted, air bubbles evacuated and nodule injected without any delay. Care will be taken to ensure that none of the IMP is lost during the transfer. Transfer of the IMP will be done immediately prior to use.

*Also see section 8.4.*

#### **9.4. Compliance with Trial Treatment**

In **Part 1** compliance will not be applicable as treatment is completed in a single visit and administered by a trial healthcare professional. We will record administration of the IMP in the CRF with details of the dose, date and time, and ease of injection. Ease of injection will be recorded as 1 (easy), 2 (moderately easy) or 3 (difficult).

In **Part 2** compliance will be defined as attending not less than 75% of injection visits i.e. 3 visits. All injections will be administered by a trial healthcare professional. We will record administration of the IMP in the CRF with details of the dose, date, and ease of injection. Ease of injection will be recorded as 1 (easy), 2 (moderately easy) or 3 (difficult).

#### **9.5. Accountability of the Trial Treatment**

Pharmacy at each site will account for the drug and placebo. Any unused, partly used or used IMP including packaging will be stored separately from IMP awaiting allocation for accountability. Accurate records will be kept for all trial products by pharmacy at each site.

#### **9.6. Concomitant Medication**

Concomitant administration with biologic DMARDs is contraindicated. For Part 1 only, coumarin anticoagulants are contraindicated. Participants may receive concurrent vaccinations but must avoid the use of live vaccines for 12 weeks after their last injection.

Throughout the study Investigators may prescribe any concomitant medications or treatments deemed necessary to provide adequate supportive care. Any medication, other than the study medication taken during the study will be recorded in the CRF.

#### **9.7. Post-trial Treatment**

**Part 1:** Participants transfer to normal care for surgery and remain in normal care. There will be no provision of the IMP beyond the trial period.

**Part 2:** Participants will transfer to normal care at the finish of the trial. There will be no provision of the IMP beyond the trial period.

### **10. SAFETY REPORTING**

### 10.1. Definitions

Adverse Event (AE)	Any untoward medical occurrence in a participant to whom a medicinal product has been administered, including occurrences which are not necessarily caused by or related to that product.
Adverse Reaction (AR)	
An untoward and unintended response in a participant to an investigational medicinal product which is related to any dose administered to that participant.
 
The phrase "response to an investigational medicinal product" means that a causal relationship between a trial medication and an AE is at least a reasonable possibility, i.e. the relationship cannot be ruled out.
 
All cases judged by either the reporting medically qualified professional or the Sponsor representative as having a reasonable suspected causal relationship to the trial medication qualify as adverse reactions.

Serious Adverse Event (SAE)	
A serious adverse event is any untoward medical occurrence that:
 
 
• results in death
 
• is life-threatening
 
• requires inpatient hospitalisation or prolongation of existing hospitalisation
 
• results in persistent or significant disability/incapacity
 
• consists of a congenital anomaly or birth defect.
 
 
Other 'important medical events' may also be considered serious if they jeopardise the participant or require an intervention to prevent one of the above consequences.
 
NOTE: The term "life-threatening" in the definition of "serious" refers to an event in which the participant was at risk of death at the time of the event; it does not refer to an event which hypothetically might have caused death if it were more severe.

Serious Adverse Reaction (SAR)	An adverse event that is both serious and, in the opinion of the reporting Investigator, believed with reasonable probability to be due to one of the trial treatments, based on the information provided.
Suspected Unexpected Serious Adverse Reaction (SUSAR)	A serious adverse reaction, the nature and severity of which is not consistent with the information about the medicinal product in question set out in the summary of product characteristics (SmPC) for the IMP.

NB: to avoid confusion or misunderstanding of the difference between the terms "serious" and "severe", the following note of clarification is provided: "Severe" is often used to describe intensity of a specific

event, which may be of relatively minor medical significance. "Seriousness" is the regulatory definition supplied above.

Any pregnancy occurring during the clinical trial and the outcome of the pregnancy will be recorded and followed up for congenital abnormality or birth defect, at which point it would fall within the definition of "serious".

#### **10.2. Causality**

The relationship of each adverse event to the trial medication will be determined by a medically qualified individual according to the following definitions:

**Related:** The adverse event follows a reasonable temporal sequence from trial medication administration. It cannot reasonably be attributed to any other cause.

**Not Related:** The adverse event is probably produced by the participant's clinical state or by other modes of therapy administered to the participant.

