#### **10.3. Procedures for Recording Adverse Events**

The safety profile of Adalimumab is well known, with the most common adverse reactions being mild injection site reactions (see section 4). Common Terminology Criteria for Adverse Events (CTCAE) v4.0 (U.S. Department of Health and Human Services) will be used to guide recording Adverse Events including grading of the event.

**Part 1.** All AEs graded 3 and above occurring during the trial and until 12 weeks **after surgery** that are observed by the Investigator or reported by the participant will be recorded on the CRF, whether or not attributed to trial medication.

**Part 2.** All AEs graded 3 and above occurring during the trial until 28 days after the last injection of trial medication that are observed by the Investigator or reported by the participant and are attributed to trial medication or the injection of the trial medication will be recorded on the CRF. The capture all of AEs in the trial CRFs is deemed not necessary due to the period of time for which the IMP has had a marketing authorisation and it's well established safety profile.

The following information will be recorded: description, date of onset and end date, severity, reason for seriousness, assessment of relatedness to trial medication, other suspect drug or device and action taken. Follow-up information should be provided as necessary.

AEs considered related to the trial medication as judged by a medically qualified investigator will be followed either until resolution, or the event is considered stable.

It will be left to the Investigator's clinical judgment to decide whether or not an AE is of sufficient severity to require the participant's removal from treatment. A participant may also voluntarily withdraw from treatment due to what he or she perceives as an intolerable AE. If either of these occurs, the participant must be given appropriate care under medical supervision until symptoms cease, or the condition becomes stable.

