#### **10.4. Reporting Procedures for Serious Adverse Events**

SAEs occurring after the first injection of trial treatment and up to 28 days after the last injection of trial treatment must be reported to the RIDD Trial Office. Only SAEs that are related to trial medication or the injection of the trial medication require to be reported. The reporting of SAEs not related to the IMP/injection is deemed not necessary due to the period of time for which the IMP has had a marketing authorisation and it's well established safety profile.

SAEs must be recorded on the trial specific SAE form and reported within 24 hours of the Site Study Team becoming aware of the event. Causality must be assessed by a medically qualified doctor. The SAE form must be sent to the Trial Office. Details are as follows:

Trial Office contact: [contact] [contact]

The Trial Office will review the information on the SAE and raise immediate queries for any key data which is missing. In the event where the reporting site does not provide an assessment of causality the Trial Office will assume that the event is related to the IMP.

The SAE form will also be sent to an independent clinician as soon as all the relevant information is available but no later than 3 calendar days from when the Trial Office is made aware of the event as per OCTRU SOPs for safety reporting. The independent clinician will assess the SAE for causality and expectedness and provide a response as per OCTRU safety reporting. In the event where the independent clinician disagrees with the assessment of the site PI, a discussion will be encouraged between the two to re-assess the event. If either the PI or the independent clinician continue to assess the event as related, both assessments will be recorded. If the event is also related and unexpected this will be reported as a SUSAR by the Trial Office or delegate to the relevant Competent Authorities, UK Ethics, Sponsor and other bodies in with the nation and local regulations of participating sites, as per below.

All SAEs will be followed till resolved or no further information is expected. SAEs will only be considered closed when signed off by the local PI.

SAEs will be reviewed at the next Safety Committee meeting (Part 1) or Data and Safety Monitoring Committee meeting (Part 2).

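### Protocol 10.2 sets a stricter test for a related event than 10.1 or the SAP, so mixed-cause events in Part 2 can go unrecorded

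*Protocol*

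**What the plan says.** **Definitions (Protocol 10.1).** An adverse reaction is a response for which "a causal relationship between a trial medication and an AE is at least a reasonable possibility, i.e. the relationship cannot be ruled out". A serious adverse reaction is worded differently, as an event "believed with reasonable probability to be due to one of the trial treatments" in the reporting investigator's opinion.

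**Assessment (Protocol 10.2).** "The relationship of each adverse event to the trial medication will be determined by a medically qualified individual according to the following definitions". *Related* requires a reasonable time sequence and a second condition: "It cannot reasonably be attributed to any other cause". *Not Related* reads: "The adverse event is probably produced by the participant's clinical state or by other modes of therapy administered to the participant". There is no third category.

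**Capture (Protocol 10.3 and 10.4).** In Part 2, adverse events of grade 3 or above, up to 28 days after the last injection, that "are attributed to trial medication or the injection of the trial medication will be recorded on the CRF". The word *attributed* is not defined. In Part 1 there is no causality condition on recording adverse events. For serious events: "Only SAEs that are related to trial medication or the injection of the trial medication require to be reported".

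**SAP, safety analysis (within section 6.4).** SAEs that are potentially related must be recorded. Related SAEs and SUSARs are compared between arms if numbers allow, and a further category for any SAE is also compared.

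**The concern.** If every event were collected, a strict causality label would do little harm, because it could be reassessed later. In Part 2 the label decides whether the event enters the safety data at all, so the threshold has to mean the same thing in every section. It does not. The 10.1 test asks whether the drug can be excluded. The 10.2 test asks whether everything else can be excluded.

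The events caught between the two tests include one kind that the documents themselves name as a risk: the Protocol background and SAP section 2.1 both say that adalimumab may increase susceptibility to infections. An infection will often have another reasonable explanation. If sites follow 10.2 literally, such an event may reach neither the adverse event CRF nor the SAE form. It would then be absent from the independent clinician's review, the DSMC's review, the SUSAR assessment and the SAP's comparison between randomised arms.

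**Working it through.** No arithmetic bears on the conflict itself, and the plan gives no figure to reproduce. The check sets the wordings side by side for a Part 2 event that is inside the 28-day window, follows the injection in a reasonable time sequence, and is either grade 3 or above or serious.

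| Status of another cause | Adverse reaction under 10.1? | Category under 10.2 | Captured if 10.2 governs 10.3 and 10.4? |
|---|---|---|---|
| No other reasonable cause | Yes | Related | Yes |
| Plausible, not probable; drug not ruled out | Yes | Neither | Nothing requires it |
| Probable; drug still a reasonable possibility | Yes | Not Related | No |
| Drug link ruled out, another cause probable | No | Not Related | No |

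The first and last rows agree under every wording. The two middle rows do not. There the event is an adverse reaction under 10.1 and, if serious, potentially related in the SAP's sense, yet it does not meet the 10.2 test for *Related*. Capture therefore depends on which text a site applies.

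**Do the downstream safeguards close the gap?** Protocol 10.4 provides three:

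- The independent clinician reassesses causality, but sees only SAE forms that have been sent in.
- An SAE with no site causality assessment is assumed related, but only once it has been reported.
- An event stays related if either the site PI or the independent clinician holds that view, which again presupposes submission.

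The sponsor representative's judgement in 10.1 has the same limit. None of these reaches an event that the site screened out.

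**What is not affected?** Local effects go on the injection site response form after each injection, whatever their cause, and the SAP compares these between arms. The grade 3 limit on adverse events and the 28-day window exclude events independently of the causality wording.

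**Can an amendment still change capture?** The SAP (section 3.1) gives the end of recruitment as 12 April 2019 in the Netherlands, the later country. Assuming a baseline visit at about that date, nine months gives 12 January 2020, the four-week visit window gives 9 February 2020, and 28 days more gives 8 March 2020. If the full 12 weeks allowed between screening and baseline are added, the date is 31 May 2020. SAP version 2.0 is dated 7 January 2021, and its Appendix 6 says all participants had completed treatment by the pandemic. By that version the window had closed.

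**The case against.** The strongest reply is that 10.1 only defines a term and is not a recording rule, so two thresholds do not both decide what is recorded. That is correct. The defect is that the operative definition in 10.2 is stricter than the term it should implement and is incomplete, and that *attributed* in 10.3 is left open.

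A second reply is that other text points to the lower bar. The SAP says potentially related. The disagreement procedure in 10.4 allows for SAEs that the site PI thought unrelated. The fields listed in 10.3 include another suspect drug or device. This shows that the authors may have intended the lower bar. It does not tell a site to set 10.2 aside, and the suspect-drug field also serves Part 1, where recording has no causality condition.

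Third, restricted capture was deliberate and is justified by the drug's established safety profile. That choice is not in dispute here. It makes a single meaning of *related* more important.

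Two stronger readings are tempting, and the documents do not support them. A reader might infer that 10.2 classes any event with a plausible other cause as *Not Related*. It does not, because that category needs the other cause to be probable; with a merely plausible cause the event is unclassified. A reader might also infer that a missed event is lost beyond recovery. Protocol 8.6 records any change in health or medication at every visit, and 9.6 puts all non-study medication in the CRF. A treated infection would normally leave some trace there. Such a trace is not a graded, causally assessed adverse event record, but it rules out the absolute claim.

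**Conclusion.** The inconsistency is in the current text and affects Part 2 safety capture. Followed literally, 10.2 does not require capture of some events that 10.1 calls adverse reactions and, for SAEs, that the SAP expects to see. The exposure is confined to mixed-cause, mainly non-local events that already pass the grade or seriousness filter and fall within 28 days of the last injection. The efficacy analysis is not touched.

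The number of events cannot be estimated, because the documents give no event rates and do not say which wording sites used. If every site applied the 10.1 threshold in practice, nothing was lost. If sites applied 10.2, the safety comparison omits these events. Separately, and under either wording, the SAP's any-SAE category cannot cover all SAEs when only related ones are reported.

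**What to change.** Use one relatedness threshold in Protocol 10.1 (including the serious adverse reaction definition), 10.2, 10.3 and 10.4 and in the SAP safety analysis. It should be the one 10.1 already states for an adverse reaction. Reword 10.2 so that an event with a possible alternative cause has a category and is captured, and define *attributed* in 10.3 by the same test. The restriction to related events can stay.

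Where the capture window has closed, state in the safety report which threshold sites applied and the limitation that follows. State also, in the SAP and the report, that the any-SAE category covers only SAEs reported as related.

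The cost is a wording amendment and a reminder to sites, with slightly more events recorded. After the window has closed, it is a query to the three centres and a short passage in the report.
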